6.1.2. Sensitivity/Supplementary Analyses

Supplementary Analysis:

- A supplementary analysis of the primary endpoint will be conducted using MMRM in PP analysis set.

6.2. Secondary Endpoint(s)

6.2.1. Time to 2 Consecutive Negative Rapid Antigen Test Results Obtained at least 24(-2)h Apart through Day 28

The event of 2 consecutive negative rapid antigen test results obtained at least 24(-2)h apart through Day 28 is defined as achieving two consecutive non-missing rapid antigen test with negative results through Day 28, where the two tests are at least 22 hours and at most 7 days apart. For the event of 2 consecutive negative rapid antigen test results obtained at least 24(-2)h apart through Day 28, the date of the first negative rapid antigen test result will be considered the First Event Date.

Time to 2 consecutive negative rapid antigen test results obtained at least 24(-2)h apart for the purpose of this study is defined as:

- For a participant achieving the event, time to event will be calculated as (First Event Date) – (First Dose Date) +1.
- For a participant not achieving the event (censored), censoring date will be at the last date of rapid antigen test measurement, and time will be calculated as (Censoring Date) – (First Dose Date) +1 or Day 27 whichever occurs first (Day 27 is the last possible day to achieve 2 consecutive negative rapid antigen test results obtained at least 24(-2)h apart through Day 28).

Participants who are hospitalized for the treatment of COVID-19 or die from any cause during the 28-day period will be classified as not achieving the event and will be censored at Day 27.

Cox proportional hazard model analyses will be used for time to 2 consecutive negative rapid antigen test results obtained at least 24(-2)h apart in mITT analysis set. Cox proportional hazard model will include treatment, geographic region, baseline viral load (< 4 or ≥ 4) and time since the last vaccination (≤ 6 months, > 6 months or unvaccinated) as appropriate. The treatment group comparison will be presented as the estimate of the hazard ratio, 95% CI and p-value. In addition, time to 2 consecutive negative rapid antigen test results obtained at least 24(-2)h apart will be summarized graphically using Kaplan-Meier plots for each of the treatment groups in mITT analysis set.

The log-rank test will be performed as additional analysis to compare the treatment group using mITT analysis set.

Similar analyses for time to 2 consecutive negative rapid antigen test results obtained at least 24(-2)h apart will also be performed in the mITT1 analysis set.

6.2.2. Time (days) to Sustained Alleviation of All Targeted Signs and Symptoms through Day 28

Sustained alleviation of all targeted COVID-19 signs/symptoms is defined as the event occurring on the first of 2 consecutive days when all symptoms scored as moderate or severe at study entry are scored as mild or absent AND all symptoms scored mild or absent at study entry are scored as absent. The first day of the 2 consecutive-day period will be considered the First Event Date.

For symptoms with no reported severity in baseline, the symptom will have to be absent in order to be counted as sustained alleviated (missing severity at baseline will be treated as mild).

Day 27 is the last possible day that symptom alleviation can be achieved (definition includes data from the subsequent day) and Day 28 is the last day participants report their daily signs and symptoms.

The time to sustained symptom alleviation for the purpose of this study is defined as:

- For a participant with sustained symptom alleviation, time to event will be calculated as (First Event Date) – (First Dose Date) +1.
- For a participant that either completes Day 28 of the study or discontinues from the study before Day 28 without sustained symptom alleviation(censored), censoring date will be at the last date on which symptom alleviation is assessed, and time will be calculated as (Censoring Date) – (First Dose Date) +1 or Day 27 whichever occurs first.

Participants who are hospitalized for the treatment of COVID-19 or die from any cause during the 28-day period will be classified as not achieving sustained symptom alleviation and will be censored at Day 27.

Cox proportional hazard model analyses will be used for time to sustained symptom alleviation in mITT analysis set. Cox proportional hazard model will include treatment, geographic region baseline viral load (< 4 or \geq 4) and time since the last vaccination (\leq 6 months, $>$ 6 months or unvaccinated) as appropriate. The treatment group comparison will be presented as the estimate of the hazard ratio, 95% CI and p-value. In addition, time to sustained symptom alleviation will be summarized graphically using Kaplan-Meier plots for each of the treatment groups in mITT analysis set.

Similar analyses for time to sustained symptom alleviation will also be performed in the mITT1 analysis set.

6.2.3. Incidence of Treatment Emergent Adverse Events (TEAEs); Incidence of SAEs and AEs Leading to Discontinuation

The incidence of TEAEs will be summarized by treatment group, by System Organ Class (SOC) and preferred term (PT) using the SAS.

The incidence of SAEs and AEs leading to discontinuation will be summarized by treatment group using the SAS.

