Visit Window	Day -1 to Day 1	0 days	±1 day	±1 day	±1 day	±2 days	±2 days	±2 days	±3 days	±7 days	±7 days	±5 days		
 • Screening procedures may be done from Day -1 to Day 1 and may be completed on the same calendar day as Baseline/Day 1 procedures. If screening and baseline visits are conducted on the same calendar day, assessments and procedure that are listed to occur at both visits only need to be completed once.
														
 • during the visit to ensure proper sample collection under observation by site staff. • Will be self-collected by the participant. • See Section 8.1.3. • See Section 8.7.3.
Participant self-collected rapid antigen testing		Collected daily and witnessed by the site staff.*										•		
 • Site staff should train participants/caregiver at the screening/baseline visit to ensure participants can perform the rapid antigen test appropriately. The participant should perform the baseline rapid antigen testing assessment during the visit to ensure proper sample collection. • Only 1 rapid antigen test is expected to be performed daily. When onsite, rapid antigen testing will be done at the site and no self-collected rapid antigen testing at home will be done. • Site staff will observe the participant performing the rapid antigen test (ie, via video or videoconferencing software if the procedure is conducted remotely), confirm testing, and record the test result in the CRF. • *Daily testing will stop once the participant has 2 consecutive negative tests separated by at least 24[-2]h. Thereafter, rapid antigen

Table 1. Study Schedule of Assessment

Visit Identifier	Screen	Treatment Period			Efficacy and Safety Follow-up Period						LTFU			Notes
		Baseline (Day 1)	Day 3	Day 5	Day 10	Day 15	Day 21	Day 28	Day 34	Week 12	Week 24	ET (prior to Day 34)		
Abbreviations used in this table may be found in Appendix 12 .														
 Day relative to start of study intervention (Day 1). Baseline (Day 1) visit is a mandatory visit. Assessments indicated in brackets [X] are only to be conducted if indicated as described in the “Notes”.

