9.3.3. Secondary Endpoints

9.3.3.1. Time to 2 consecutive negative rapid antigen test results obtained at least 24(-2)h apart through Day 28

For the event of 2 consecutive negative rapid antigen test results obtained at least 24(-2)h apart through Day 28, the date of the first negative rapid antigen test result will be considered the First Event Date.

Time to 2 consecutive negative rapid antigen test results obtained at least 24(-2)h apart for the purpose of this study is defined as:

- For a participant achieving the event, time to event will be calculated as (First Event Date) – (First Dose Date) +1.
- For a participant not achieving the event (censored), censoring date will be at the last date of rapid antigen test measurement, and time will be calculated as (Censoring Date) – (First Dose Date) +1 or Day 27 whichever occurs first (Day 27 is the last

possible day to achieve 2 consecutive negative rapid antigen test results obtained at least 24(-2)h apart through Day 28).

Cox proportional hazard model analyses will be used for time to 2 consecutive negative rapid antigen test results obtained at least 24(-2)h apart in mITT analysis set. Cox proportional hazard model will include treatment, geographic region and potential covariates as appropriate. The treatment group comparison will be presented as the estimate of the hazard ratio, 95% CI and p-value. In addition, time to 2 consecutive negative rapid antigen test results obtained at least 24(-2)h apart will be summarized graphically using Kaplan-Meier plots for each of the treatment groups in mITT analysis set.

Similar analyses for time to 2 consecutive negative rapid antigen test results obtained at least 24(-2)h apart will also be performed in the mITT1 analysis set.

9.3.3.2. Time (days) to sustained alleviation of all targeted signs and symptoms through Day 28

Sustained alleviation of all targeted COVID-19 signs/symptoms is defined as the event occurring on the first of 2 consecutive days when all symptoms scored as moderate or severe at study entry are scored as mild or absent AND all symptoms scored mild or absent at study entry are scored as absent. The first day of the 2 consecutive-day period will be considered the First Event Date.

For symptoms with no reported severity in baseline, the symptom will have to be absent in order to be counted as sustained alleviated (missing severity at baseline will be treated as mild).

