Appendix 1. Summary of Efficacy Analyses

Endpoint	Analysis Type	Population	Data Inclusion and Rules for Handling Intercurrent Events and Missing Data	Analysis Model
Change in viral SARS-CoV-2 RNA level as measured in NP swabs from baseline to Day 5	Primary	miITT	All data collected will be included regardless of study treatment discontinuation and prohibited therapies. MMRM method to take account of missing at random.	MMRM
Change in viral SARS-CoV-2 RNA level as measured in NP swabs from baseline to Day 5	Secondary	miITT1	All data collected will be included regardless of study treatment discontinuation and prohibited therapies. MMRM method to take account of missing at random.	MMRM
Change in viral SARS-CoV-2 RNA level as measured in NP swabs from baseline to Day 5	Supplementary	PP	MMRM method to take account of missing at random.	MMRM
Change in viral SARS-CoV-2 RNA level as measured in NP swabs from baseline to Day 5	Subgroup analyses for the primary endpoint	miITT	All data collected will be included regardless of study treatment discontinuation and prohibited therapies. MMRM method to take account of missing at random. Subgroups defined in Section 6.4	MMRM

Endpoint	Analysis Type	Population	Data Inclusion and Rules for Handling Intercurrent Events and Missing Data	Analysis Model
Time to 2 consecutive negative rapid antigen test results obtained at least 24(-2)h apart through Day 28	Secondary	mITT mITT1	All data collected will be included regardless of study treatment discontinuation and prohibited therapies. Missing data will not be imputed.	Cox proportional hazard model; KM curves; Log-rank test
Time (days) to sustained alleviation of all targeted signs and symptoms through Day 28	Secondary	mITT mITT1	All data collected will be included regardless of study treatment discontinuation and prohibited therapies. Missing data will not be imputed.	Cox proportional hazard model; KM curves
Proportion of participants with SARS-CoV-2 RNA in NP swab below the LLOQ on Days 3, 5, 10, 15, 21, 28, and 34	Exploratory	mITT	Missing data will not be imputed.	Descriptive summary
Proportion of participants with sustained NP swab SARS-CoV-2 RNA below the LLOQ (defined as <2.0 log ₁₀ copies/mL) from Day 5 through Day 34	Exploratory	mITT	Missing data will not be imputed.	Descriptive summary

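### Read literally, the antigen-clearance rule in SAP 6.2.1 lets an extra negative test taken less than 22 h after the first one postpone the event date, usually by one day

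*SAP*

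**What the plan says.** SAP 6.2.1 describes the event thus: "achieving two consecutive non-missing rapid antigen test with negative results through Day 28, where the two tests are at least 22 hours". The same sentence caps the gap at 7 days. Protocol 9.3.3.1 sets the event date, and SAP 6.2.1 repeats it: "the date of the first negative rapid antigen test result will be considered the First Event Date". Protocol 9.3.3.1 itself has neither the non-missing condition nor the 7-day limit.

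The testing schedule is in Table 1 (Protocol 1.3):
- On frequency: "Only 1 rapid antigen test is expected to be performed daily".
- On the place of testing on visit days: "When onsite, rapid antigen testing will be done at the site and no self-collected rapid antigen testing at home will be done".
- On stopping: "Daily testing will stop once the participant has 2 consecutive negative tests separated by at least 24[-2]h".

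For this endpoint, SAP Appendix 1 adds: "Missing data will not be imputed".

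Neither document sets a clock time for the antigen test. The instruction in Protocol 8.2.1 to keep to about the same time each day concerns the diary. SAP Appendix 2.1 resolves conflicting antigen results on one day, but not two negatives on neighbouring days that are less than 22 h apart.

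The endpoint is one of the two key secondary endpoints tested by the Hochberg method (Protocol 9.1.2, SAP 5.1).

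**The concern.** Once-daily tests alternate between clinic and home, so the gap between neighbouring tests can easily be less than 22 h. The literal rule then rejects the pair. It also gives no way for a later negative to confirm the first one across the negative that lies between them. If that middle test is missing, the outer two become consecutive non-missing tests and the earlier date stands.

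A definition of clearance should not give a later date because one more negative was observed. Here the date depends partly on appointment times and missed tests as well as on when antigen disappears. The endpoint is counted in whole days, so a one-day shift is its smallest possible error and is visible in the curves.

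**Working it through.** **The plan's own figure.** The documents give no event count or power for this endpoint. The only sample-size figure is for the primary endpoint, and it reproduces. Control n = (1 + 1/2) × 1.8² × (1.960 + 1.282)² / 0.7² = 104.2, rounded up to 105. The total is 3 × 105 = 315, with power 90.2%. Then 315 / (0.90 × 0.85) = 411.8, against 411 stated. The antigen rule does not affect it.

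**Two rules compared.**
- Literal: the first adjacent pair of non-missing negatives with a gap of 22 to 168 h, second test by Day 28; the event day is that of the first test.
- Alternative: the first negative followed by any negative 22 to 168 h later, by Day 28, with no positive between; the event day is that of the first negative.

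**Worked example.** Positive through Day 4, clinic negative on Day 5, home negatives at 08:00 on Days 6 and 7. With the clinic test at hour h, the Day 5 to Day 6 gap is 24 + 8 − h.

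| Day 5 clinic time | Gap to Day 6 | Literal | Literal, Day 6 missed | Alternative |
|---|---|---|---|---|
| 08:00 | 24 h | Day 5 | Day 5 | Day 5 |
| 10:00 | 22 h | Day 5 | Day 5 | Day 5 |
| 11:00 | 21 h | Day 6 | Day 5 | Day 5 |
| 14:00 | 18 h | Day 6 | Day 5 | Day 5 |
| 16:00 | 16 h | Day 6 | Day 5 | Day 5 |

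At 14:00, Day 5 to Day 7 is 18 + 24 = 42 h. That is long enough, but the two tests are not adjacent unless Day 6 is missing. The stop rule in Table 1 does not prevent this. An 18 h pair does not end daily testing, so the Day 7 test is taken.

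**Frequency under assumed clock times.** These times are not in the documents. Conversion is exponential with a median of 3, 5 or 8 days. Ranges cover the three medians and repeated runs.

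| Home tests | Clinic tests | Events dated late under the literal rule |
|---|---|---|
| about 08:00 (SD 1 h) | 09:00–16:00 | 29–38% (mean delay 0.31–0.39 days over all events) |
| same, 10% of home tests missed | 09:00–16:00 | 28–34% |
| about 08:00 (SD 1 h) | 09:00–12:00 | 22–28% |
| about 12:00 (SD 2 h) | 09:00–16:00 | 25–27% |
| 12:30 (SD 0.5 h) | 09:00–16:00 | 12–16% |
| 12:30 (SD 0.5 h) | 11:00–14:00 | about 1% |
| 10:30 (SD 0.5 h) | 09:00–12:00 | about 1% |

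Home tests well after clinic hours create the same problem in the other direction, because the gap from an evening home test to the next day's clinic test is short.

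**Effect on the hazard ratio.** Assumptions: 411 participants randomized 2:1, daily clearance hazard 0.12 on placebo, true hazard ratio 1.0 or 1.3, clinic tests on Days 3, 5, 10, 15, 21 and 28. A share q of clinic tests is at 14:00 and all other tests are at 08:00.

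| q | Participants whose date differs |
|---|---|
| 0.1 | about 3% |
| 0.3 | about 8% |
| 0.5 | 13–14% |
| 1 | 26–28% |

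The largest movement in the mean estimated hazard ratio was at q = 1 with a true value of 1.3: 1.271 under the literal rule and 1.283 under the alternative, a difference of 0.012. With a true value of 1.0 and q = 1 the two were 1.031 and 1.034.

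**The case against.** The strongest reply is that this may rarely happen. Table 1 has site staff witness the home tests, by video if remote, and record the results. Staff must be available at that time, so home tests may cluster in working hours and close to clinic times. In that case only about 1% of events move. This stands as a reason not to quote a single high percentage. It does not remove the problem, because witnessing sets no clock time.

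A second reply is that adjacent, well-spaced tests match the operational stop rule in Table 1. That is true of when to stop testing, but it does not require the analysis to date clearance from a later negative. A third is that consecutive could mean no positive in between, which the wording of Protocol 9.3.3.1 leaves open. If that is the intention, the SAP should say so, because two programmers could produce different dates from the present text.

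A reader might infer more than the documents support:
- *That the treatment comparison is biased.* Participants and site staff are blinded and both arms share one visit schedule, so the shift should be similar in both. A difference between arms is conjecture, and the calculated change in the hazard ratio is small.
- *That the rule encourages missed tests.* A blinded participant gains nothing from an earlier date. The effect needs a first negative, a second negative less than 22 h later, and then a further adequately spaced negative.
- *That the early second negative is thrown away.* It is kept and becomes the first test of the next pair. What is lost is the short-gap pair, and with it the earlier date.

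**Conclusion.** The definition is flawed as written: under the literal reading an additional negative postpones the event, usually by one day, and a missing test restores the earlier date. This follows from the text alone and needs no assumption beyond reading consecutive as adjacent.

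Its size does rest on assumptions. The share of events affected cannot be found from the documents. It ranges from about 1% to about one third or somewhat more, depending on how far home and clinic times differ. The expected effect on the hazard ratio is about 0.01, so the Hochberg-tested comparison is not seriously threatened. The main effect is on the event dates, the Kaplan-Meier curves and the reported time to clearance. It should be corrected because the endpoint is a key secondary one and the correction is cheap.

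**What to change.** Before unblinding, restate the event in SAP 6.2.1 as follows: the first negative rapid antigen test that is followed by another negative test at least 22 h and at most 7 days later, through Day 28, with no positive result in between; the event is dated at that first negative test.

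This keeps the 22 h minimum, the 7-day limit and first-negative dating. Any pair that qualifies now still qualifies, so no participant loses an event or gets a later date. The cost is one sentence and a small programming change. It needs no new data and no change to the testing schedule.

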Arm Title	Nirmatrelvir/ritonavir	Placebo/ritonavir
Arm Type	Experimental	Other
Arm Description	Participants will receive nirmatrelvir/ritonavir 300 mg/100 mg (or 150 mg/100 mg for participants with eGFR \geq 30 to $<$ 60 mL/min/1.73 m 2 or eCrCl \geq 30 to $<$ 60 mL/min) q12h from Day 1 through Day 5.	Participants will receive placebo 0 mg/ritonavir 100 mg q12h for 5 days.

Statistical Methods:

The study will randomize approximately 411 participants in a 2:1 randomization ratio to nirmatrelvir/ritonavir or placebo/ritonavir.

The primary efficacy endpoint is the change in viral SARS-CoV-2 RNA level from baseline to Day 5 as measured in NP swabs. This will be estimated without regard to study treatment discontinuation and without regard to prohibited therapies.

With respect to the primary endpoint of change in SARS-CoV-2 RNA level from baseline to Day 5 as measured in NP swab in the mITT analysis set, and assuming a SD of 1.8 (based on Study C4671005 [EPIC-HR, NCT04960202]), a sample size of approximately 315 evaluable participants (210 participants in the nirmatrelvir/ritonavir group and 105 participants in the placebo/ritonavir group) is expected to provide 90% power to detect a difference of 0.7 log₁₀ copies/mL in viral RNA between groups using a 2-sided 0.05 alpha level test. Assuming approximately 10% of participants will have a negative viral RNA result at baseline, and assuming a non-evaluable rate of 15%, approximately 411 participants will be randomized in the study to achieve approximately 315 participants evaluable for the primary efficacy endpoint.

No formal interim analysis is planned for this study. However, the sponsor may conduct unblinded reviews of the data during the course of the study if requested by regulatory

[figure not shown]
authorities including in the support of regulatory submissions. Should an unblinded review be requested, details of the unblinding plan will be described in the SAP and a separate data unblinding document.

Ethical Considerations:

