4. STUDY DESIGN

4.1. Overall Design

This Phase 2, randomized, double-blind, placebo-controlled study will evaluate the efficacy and safety of a repeat 5-day treatment course of nirmatrelvir/ritonavir or placebo/ritonavir for the treatment of mild-to-moderate COVID-19. Participants must have written documentation, such as an electronic health record, medical record, or prescription receipt of treatment with nirmatrelvir/ritonavir (verbal assertion of treatment is not acceptable) with patient-reported 100% compliance (ie, completed a 5 day course of nirmatrelvir/ritonavir). They must have experienced alleviation or resolution in COVID-19 signs/symptoms followed by a worsening (rebound) of signs/symptoms along with a positive rapid antigen test after completing an initial 5-day course of nirmatrelvir/ritonavir. The onset of rebound in COVID-19 symptoms along with evidence of SARS-CoV-2 infection must occur within 2 weeks (14 days) after completion of an initial 5-day course of nirmatrelvir/ritonavir.

Eligible participants for this study will be randomly assigned (2:1 allocation of active to placebo) to receive:

- nirmatrelvir plus ritonavir orally q12h for 5 days; or
- placebo plus ritonavir orally q12h for 5 days.

Randomization will be stratified by geographic region.

Participants will be screened within 24 hours before randomization.

Participants must be randomized within 48 hours from the onset of the rebound COVID-19 symptoms and must be randomized within 24 hours of a positive baseline rapid antigen test. The total study duration is up to 24 weeks, including study intervention administration through Day 5 or Day 6, efficacy and safety assessments through Day 34, and long-term follow up at Weeks 12 and 24.

Participants are eligible if they are at least 12 years of age (and weigh ≥ 40 kg at screening) and have at least 1 characteristic or underlying medical condition associated with an increased risk of developing severe illness from COVID-19. However, participants who are immunocompromised are excluded from this study as they may have prolonged viral shedding due to their immunocompromised state[14,15]. Participants will be eligible for enrollment irrespective of COVID-19 vaccination/boosted status (except for time course restrictions listed in the exclusion criteria).

An independent E-DMC will review unblinded data to ensure the safety of participants on an ongoing basis throughout the duration of the study.

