2.1. Modifications to the Analysis Plan Described in the Protocol

Not Applicable.

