2.2. Study Objectives, Endpoints, and Estimands

Objectives	Endpoints	Estimands
Primary:	Primary:	Primary:

 To compare the effect of nirmatrelvir/ritonavir to placebo/ritonavir on viral RNA level in NP swabs in participants with mild-to-moderate COVID-19. 	
 The change in viral SARS-CoV-2 RNA level as measured in NP swabs from baseline to Day 5. 	
 The difference in mean change of SARS-CoV-2 RNA level in NP swabs from baseline to Day 5 between nirmatrelvir/ritonavir and placebo/ritonavir group in participants with a rebound in COVID-19 symptoms and a positive rapid antigen test within 2 weeks following completion of an initial 5-day treatment course ,who have a positive viral RNA NP swab test result at baseline. This will be estimated without regard to study treatment discontinuation and without regard to prohibited therapies.

Objectives	Endpoints	Estimands
Secondary:	Secondary:	Secondary:

 To compare the effect of nirmatrelvir/ritonavir to placebo/ritonavir on the duration of viral shedding. 	
 Time to 2 consecutive negative rapid antigen test results obtained at least 24 (-2) h apart through Day 28. 	
 The hazard ratio for time to 2 consecutive negative rapid antigen test results obtained at least 24 (-2) h apart through Day 28 between nirmatrelvir/ritonavir and placebo/ritonavir group in participants with rebound in COVID-19 symptoms and a positive rapid antigen test within 2 weeks following completion of an initial 5-day treatment course, who have a positive viral RNA NP swab test result at baseline. This will be estimated without regard to study treatment discontinuation and without regard to prohibited therapies.

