2.4. Sample Size Determination

The study will enroll approximately 411 participants.

The sample size calculation is based on the primary efficacy endpoint as the change in viral RNA level from baseline to Day 5 as measured in NP swabs in the MITT analysis set. Assuming a SD of 1.8 (based on EPIC-HR, NCT04960202), a sample size of approximately 315 evaluable participants (210 participants in nirmatrelvir/ritonavir group and 105 participants in placebo/ritonavir group) is expected to provide 90% power to detect a difference of 0.7 \log_{10} copies/mL in viral RNA between groups using a 2-sided 0.05 alpha level test. Assuming approximately 10% of participants will have a negative viral RNA result at baseline, and assuming a non-evaluable rate of 15%, approximately 411 participants will be randomized in the study to achieve approximately 315 participants evaluable for the primary efficacy endpoint.

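### SAP 6.2.1 overwrites an antigen clearance already recorded when the participant is later hospitalised for COVID-19 or dies, a rule absent from protocol 9.3.3.1 and not declared as a change

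*SAP*

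**What the plan says.** **SAP 6.2.1** dates the event at the first of two qualifying negatives and censors everyone else at the last antigen test, Day 27 at the latest. It then adds that participants hospitalised for COVID-19, or dying of any cause, within the 28 days "will be classified as not achieving the event and will be censored at Day 27". Nothing limits this to participants who had not yet cleared.

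**Protocol 9.3.3.1** has the same event date and the same general censoring: "For a participant not achieving the event (censored), censoring date will be at the last date of rapid antigen test measurement". It contains no hospitalisation or death rule. In the protocol that rule appears only in 9.3.3.2, for symptom alleviation.

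**The objective** in SAP 2.2 is "To compare the effect of nirmatrelvir/ritonavir to placebo/ritonavir on the duration of viral shedding". The matching estimand (protocol 9.1.1.2, SAP 2.2.2) addresses only stopping study treatment and using prohibited therapies. SAP Appendix 1 says that all collected data are included for this endpoint and mentions no exception for admission or death.

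**SAP 2.1**, where departures from the protocol belong, reads "Not Applicable". Protocol section 9 allows the SAP to modify the plan where appropriate. It requires a protocol amendment only for major changes to the primary endpoint definitions or their analyses.

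**The concern.** Take a participant with witnessed negatives on Days 4 and 5 who is admitted for COVID-19 on Day 20, or who dies of an unrelated cause on Day 25. Protocol 9.3.3.1 scores an event on Day 4. SAP 6.2.1 scores no event and keeps the participant at risk to Day 27. The two governing documents give different values for the same data, and SAP 6.2.1 first assigns this participant an event date and then withdraws it.

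A later admission does not undo a completed clearance, and the design treats clearance as reached: daily antigen testing stops after two consecutive negatives (Schedule of Activities; protocol 8.7.3). COVID-19 hospitalisation or death already has its own exploratory endpoint (SAP 6.3.9).

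The endpoint is one of the two tested by Hochberg after the primary endpoint succeeds in mITT and then in mITT1 (protocol 9.1.2, SAP 5.1). With two hypotheses, a symptom p-value between 0.025 and 0.05 is rejected only if the antigen p-value is also at most 0.05. A shifted antigen result can therefore change the symptom conclusion as well.

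**Working it through.** **1. The plan's own figure.** The sample size concerns the primary endpoint only: "90% power to detect a difference of 0.7" log10 copies/mL, "using a 2-sided 0.05 alpha level test", SD 1.8, participants "randomly assigned (2:1 allocation of active to placebo) to receive" treatment.
- Control n = (1 + 1/2) × (1.960 + 1.282)² × 1.8² / 0.7² ≈ 104.2, rounded up to 105. Active 210, total 315.
- Power at 105 vs 210: 90.2% (normal), 90.0% (noncentral t).
- 315 / 0.90 / 0.85 = 411.8, against a stated 411.

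The figures reproduce and are not affected by this point. No power or event count is stated for the antigen endpoint.

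**2. Numbers in mITT.** 411 × 0.90 ≈ 370, split 2:1 into 247 and 123.

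**3. Hospitalisation or death rates.** The documents give none by arm for rebound patients. What they do give:
- First-course EPIC-HR (protocol 2.2.1): 5/697 = 0.72% vs 44/682 = 6.45%, and 9/1039 = 0.87% vs 66/1046 = 6.31%.
- The cited retrospective review (protocol 2.1): 4 rebound cases, none hospitalised.

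At 0.72% vs 6.45%, the expected numbers are 247 × 0.0072 = 1.8 and 123 × 0.0645 = 7.9 participants.

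**4. Simulation with no true antigen effect.** Clearance was exponential with the same median of 5 days in both arms, in whole days, cut at Day 27. Hospitalisation was independent of clearance time. Participants flagged as hospitalised were set to non-event at Day 27, as SAP 6.2.1 requires. Most rows come from a Cox model with treatment only and Efron ties, 500 runs per scenario. The 0.87% vs 2% row combines a 300-run Cox check (1.03) with a 3,000-run log-rank check (1.04). The median, the independence and all rates other than EPIC-HR are assumptions. A hazard ratio above 1 means faster clearance on active.

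| Active vs placebo rate | HR under the SAP rule |
|---|---|
| 3% vs 3% (assumed) | 1.00 |
| 0.87% vs 2% (placebo rate assumed) | 1.03–1.04 |
| 0% vs 2% (assumed) | 1.07 |
| 0.87% vs 6.31% (first course) | 1.18–1.20 |
| 0.72% vs 6.45% (first course) | 1.20 |
| 6.45% vs 0.72% (reversed) | 0.84 |

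At 0% vs 2%, 8–11% of runs falsely favoured active, against a nominal 2.5%. At 0.87% vs 2%, two-sided p<0.05 occurred in 6.6% of the 3,000 runs, against 4.6% with no override.

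**5. How much comes from overwriting.** At 0.72% vs 6.45%, suppose half of those hospitalised had cleared first:
- SAP rule as written: HR 1.197.
- Observed clearances kept, the rest held as non-events to Day 27: HR 1.10.
- Observed clearances kept, the rest censored at admission (approximating the protocol's last-test rule): HR 1.01.

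On the log scale, ln 1.197 = 0.180 and ln 1.10 = 0.095. Overwriting accounts for 0.085 of 0.180, roughly half. The rest comes from holding never-cleared participants to Day 27. If all had cleared first, keeping their dates returns the HR to 1.00.

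**The case against.** **The change is permitted.** Protocol section 9 allows it for a secondary endpoint. This stands: a reader might infer that the SAP breaches the protocol, and the documents do not support that. What remains is that SAP 2.1 declares nothing and the estimand is silent.

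**The version history does not list the rule.** A reader might infer an unrecorded late change. SAP section 1 compares SAP Version 2 with Version 1; it does not list departures from the protocol. If the rule was already in Version 1, it would not appear there. The omission shows nothing.

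**A composite rule is a recognisable choice.** The SAP uses the same rule for symptom alleviation and symptom resolution. It is prespecified and applies to both arms. In patients enrolled because an apparent recovery reversed, counting a later COVID-19 admission as failure can be argued. This has force for participants who never cleared. It has less for those with completed negatives, and little for death from any cause after clearance.

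**The size is speculative.** At first-course rates about a third of null trials came out falsely significant, and a reader might infer that the antigen test is badly inflated. The documents do not support that. In EPIC-HR, first-course treatment was compared with placebo; here both arms have completed a full course. Protocol 5.2 excludes current or anticipated need for hospitalisation and hospitalisation for the index infection. Protocol 2.1 reports mild rebound without hospitalisation in the cited review, and no association of viral RNA rebound with hospitalisation or death. Two primary-endpoint tests must also succeed first, and the Hochberg threshold is 0.025 if the symptom endpoint is not significant.

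**Conclusion.** The concern holds as a fault in a stated rule, and it should be corrected. Followed literally, SAP 6.2.1 discards observed clearances on an alpha-controlled endpoint about viral shedding. It gives a participant-level result different from protocol 9.3.3.1, without declaring the change or naming the events in the estimand.

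The numerical effect is conditional. It is nil at equal rates, near zero if almost nobody is hospitalised or dies, and small to moderate at low unequal rates. It reaches about 1.2 only at rates taken from a different treatment setting. All of these figures assume a 5-day median clearance and hospitalisation independent of clearance time. If slow clearers are the ones admitted, fewer completed clearances are overwritten and more of any shift comes from the Day 27 censoring of participants who never cleared.

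A reader might infer that the rule favours nirmatrelvir/ritonavir. It does so only if hospitalisation or death is lower on active; with the rates reversed the hazard ratio falls to 0.84.

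**What to change.** - In SAP 6.2.1, keep the First Event Date for any participant whose two qualifying negatives were both completed before admission or death. Apply the Day 27 rule only to participants who had not cleared by then.
- Name that remaining composite handling of hospitalisation and death in the secondary estimand, and list it in SAP 2.1 as a change from protocol 9.3.3.1.
- Day 27 censoring of never-cleared participants can still shift the hazard ratio. Report two sensitivity analyses: last-test censoring as in protocol 9.3.3.1, and the current full override.
- Apply the same derivation to the mITT1 analysis, and settle the wording before unblinding.

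The cost is SAP wording, one extra derivation and two sensitivity runs, with no new data. The downside is a slightly less favourable hazard ratio if hospitalisation turns out lower on active.
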